
 
• Diagnosis of low vision
 
• Self-reported difficulty with mobility and finding doors (either indoors or outdoors) and using signalized crosswalks.
 
• Either sex
 
• Any self-declared ethnoracial category
 
• ≥ 14 years' old
 
• Ability to cooperate for tests
 
• Able to participate in all visits
 
	
 
• Unable to use head mounted display
 
• Unstable age-related macular degeneration within the past 3 months
 
• Unstable diabetic retinopathy within the past 3 months
 
• Unstable diabetes within the past 3 months
 
• Ocular infection or ocular inflammation in the past 3 months
 
• Ocular trauma within the past 6 months
 
• Intraocular surgery within 6 months
 
• Optical coherence tomography retinal findings of concern to investigator for unstable vision during the study
 
• Women who are pregnant (due to risk of falls and change in gait). The study team will ask if a potential subject is pregnant and those who self-report will be excluded.
 
• Uncontrolled seizure disorder in the past 6 months
 
• Cerebrovascular accident occurring in the past 6 months
 
• Parkinson disease or neurological condition that limits mobility
 
• Alzheimer disease or other forms of dementia
 
• Score of less than 18 on MoCA-Blind test
 
• Conditions of concern to investigator that would confound orientation and mobility, such as severe arthritis, pain that limits ambulatory activities, or orthopedic surgery (e.g., hand, arm, shoulder, knee, or hip surgery within 12 months)
 

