### b. Experimental Methods and Design

SmartHMD (described in section d) will be evaluated in participants (n=30) with severe VF constriction. The study visit should take up to three hours depending on which experiments are performed. Typically, we will focus on one or two of the five tests described below. For all experiments, the participant's baseline mobility skills will serve as the control. We will first train the participant to ensure they can effectively use the smartHMD. Prior to each task, we will describe the task to them. If the participant does not think they can perform the task with their baseline mobility, they will not be forced to do so. For some experiments, we will blindfold the participants, to remove the variable of residual vision. This has been done in other studies of blind mobility (Rizzo 2018).

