#### 1. Outdoor testing: crosswalk detection

We will use crosswalks with signals near the North Campus Research Center. These crosswalks are highly used by pedestrians, thus they have well-maintained signals, crosswalk striping, and pavement. Testing will be done in with verbal, vibrational, and (for Argus II participants) modified video.

Subjects will stand 2 meters from and with their backs facing the intersection. Subjects will then be instructed to walk the intersection. They will then have to align themselves with the crosswalk and point to the pedestrian signal upon locating it. Upon locating the pedestrian signal, subjects will either cross or not cross the street based on their interpretation of the pedestrian signal display (without smartHMD) or by following the cues from the smartHMD (smartHMD).. After an orientation period with the smartHMD (which will include practice mobility trials), subjects will repeat the crosswalk navigation task using smartHMD and, if possible, without smartHMD.

Approximately 12 crosswalk navigation trials will be collected for each condition. To reduce the effects of familiarity with the intersection with repeated visits and trials, four different signalized intersections will be

used and subjects will negotiate each intersection in the forward and reverse direction. The order of walking direction and which signalized intersection will be used will be counter-balanced across subjects and condition. The order of testing with the Baseline or Sham condition first will also be counter-balanced across subjects and signalized intersections.

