For all experiments, time to the complete the route is the primary outcome measure. In contrast to reaction time in speed-critical tasks, time to completion is used here as a continuous measure of task difficulty that encompasses wrong responses and resulting error correction, slow walking due to confusion, and overall efficacy of travel. Our statistical analysis will account for differences in walking speed between participants. Secondary measures include Percentage of Preferred Walking Speed (Patel 2006), # of unintended contacts with obstacles and walls, # of incorrect turns, # of requests for assistance, type of assistance requested, and # of interventions by the experimenter. Data collection will be facilitated by a wearable test system with redundant data collection via hard copy datasheets and a handheld (by an experimenter) video camera. Post-test data processing will refine the measures.

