#### **d. Data Analysis**

Data analysis will be done to determine which configuration of the smartHMD device improves O&M in study participants who have LV, and if improvements are significantly better than baseline mobility.

The peer-reviewed literature provides estimates of mean PPWS and variability within groups of LV subjects. PPWS can be viewed as a surrogate measure for completion time, and its reported variability among LV subjects is useful for sample size estimation. Other groups (Soong, 2004) have reported on two visually impaired groups ( $n=19$  &  $n=18$ ); the mean (SD) PPWS values for the two groups were 40.1% (12.7%) and 40.8% (13.1%). Thus, we estimate the SD to be 33% ( $\sim 13/41$ ) of the mean completion times for both baseline and smartHMD conditions. Our prior work (Adebiyi 2017) compared guided mobility (with verbal or vibrational feedback) versus no guidance and found significant differences in completion time with  $n=11$  participants. Thus our subject pool of 30 should be adequate to yield rigorous results.

Given the small sample size, an informative way to present the data will be through listings of the raw data. Listings will show subject disposition, demographic and baseline characteristics, extent of exposure and study termination/withdrawal information, as well as efficacy information. Descriptive statistics (number and percentage for categorical data; mean, median, standard deviation, inter-quartile range, min/max, and number for continuous data) will be presented for each evaluable for differences in outcomes control vs. smartHMD condition. For discrete variables, descriptive analyses will be based on numbers of subjects and related percentages.

Interviews will be audio-recorded, transcribed verbatim, and analyzed using inductive qualitative analysis. Additionally, mixed methods analyses, such as joint display tables, will be used to integrate qualitative findings with vision-related quality of life data from the IVI-VLV. These analytic approaches will provide insights on how user preferences vary based on vision-related quality of life across various domains.

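### Does calling a pool of 30 adequate need correcting when each participant typically does only one or two of the navigation tests?

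*Combined protocol and SAP*

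**What the plan says.** Section III.d takes an SD of 33% of mean completion time from published walking-speed data, notes that an earlier study found significant differences between guided and unguided mobility with 11 participants, and concludes: "Thus our subject pool of 30 should be adequate to yield rigorous results". It gives no target difference, significance level, power or within-person correlation. The same section aims to establish "if improvements are significantly better than baseline mobility".

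Section III.b assigns 30 participants to the study as a whole and continues: "Typically, we will focus on one or two of the five tests described below". Four tests follow, numbered 1 to 4. On the outcome, it says: "For all experiments, time to the complete the route is the primary outcome measure". Each participant's own baseline mobility is the control, but that run is optional: "If the participant does not think they can perform the task with their baseline mobility, they will not be forced to do so".

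The number of visits is not fixed. Section III.b refers to one: "The study visit should take up to three hours depending on which experiments are performed". Table 1 requires participants to be "Able to participate in all visits", and the crosswalk test mentions repetition: "To reduce the effects of familiarity with the intersection with repeated visits and trials".

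**The concern.** The adequacy statement concerns the pool, while the primary comparisons are made test by test. If participants are spread over four or five tests, the number in each could be well below 30, and optional baseline runs could reduce the complete pairs further. Nothing pools the tests, names one as principal, sets a minimum per test or says how participants are assigned.

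The 33% SD does not close the gap. It describes variation between people, whereas a within-person comparison needs the SD of the paired difference, and the plan does not carry it into any calculation.

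At stake is how to read a result that is not significant. From 30 pairs it would be fairly informative; from 6 it would say very little. A reader of the plan cannot tell which case applies to which test.

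**Working it through.** **The plan's own figures.** The two published groups give 12.7/40.1 = 31.7% and 13.1/40.8 = 32.1%; the plan's shorthand 13/41 gives 31.7%. The stated 33% is rounded up slightly, which is harmless. The figure of 30 cannot be reproduced, because no effect size, alpha, power or correlation is stated.

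**Participants per test** (even spread assumed): 30 × tests per participant ÷ number of tests.

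| Tests per participant | Four tests | Five tests |
|---|---|---|
| One | 7.5 | 6 |
| Two | 15 | 12 |

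If one or two tests is meant per visit, and there are two visits (an assumption), the figures double to 15-30 with four tests and 12-24 with five. These are averages, not limits: a test that everyone does has 30, and a neglected one could have fewer than 6.

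**Detectable difference.** Paired t-test (noncentral t), two-sided 0.05, 80% power and within-person correlation ρ, all assumed. Times are expressed relative to the baseline mean.

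- Equal SD in both conditions: SD of the difference = 0.33 × √(2(1 − ρ)). At ρ = 0.5 this is 0.33.
- SD at 33% of each condition's own mean, for a reduction d: SD of the difference = 0.33 × √(1 + (1 − d)² − 2ρ(1 − d)).

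| Pairs | Equal SD, ρ = 0.5 | Own-mean SD, ρ = 0.5 | Equal SD, ρ = 0.3 to 0.9 |
|---|---|---|---|
| 30 | 17.5% | 16.2% | 20.7% to 7.8% |
| 15 | 25.7% | 23.3% | 30.4% to 11.5% |
| 12 | 29.3% | 26.3% | 34.7% to 13.1% |
| 6 | 47.3% | 41.2% | 56.0% to 21.2% |

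Relative to 30 pairs at ρ = 0.5, the detectable difference is 25.7/17.5 = 1.47 times as large at 15 pairs and 47.3/17.5 = 2.70 times at 6. With own-mean SD the ratios are 23.3/16.2 = 1.44 and 41.2/16.2 = 2.54.

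**Against the precedent.** With equal SD and ρ = 0.5, 11 pairs detect 30.9%. At two tests per participant, the 12 to 15 pairs detect 29.3% to 25.7%, which is slightly better. At one test per participant, the 6 to 7.5 per test fall below 11.

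**Effect of correlation.** For an assumed 20% reduction with equal SD, 12 pairs give 48% power at ρ = 0.5 and 99% at ρ = 0.9. The crosswalk test plans about 12 trials per condition and door detection plans 8 trials. Averaging over trials reduces within-person noise and so tends to raise the correlation, but the plan gives no value for it.

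**The case for a change.** The strongest case for a change is that this is the plan's only sample-size justification. It promises rigour and a verdict on significance, yet 30 may not be the number in any primary comparison. The precedent does not rescue it fully: its effect size is not given, and an even spread at one test each leaves fewer than 11 per test. An effect with 80% power at 30 pairs has about 48% at 15 and 18% at 6 (equal SD). A few sentences on expected pairs per test, visits and assignment would cost nothing in participants.

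Most of the facts in this stand. The sentence is loose, and the stated number of tests does not match the number described. What does not follow is that the design fails. The low figures need both an even spread and one test each, neither of which the plan states. The text can equally be read as concentrating the study on one or two tests. Section III.d also calls the sample small in its next paragraph and turns to raw-data listings and descriptive statistics, so the plan does not rest wholly on significance tests.

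**Conclusion.** No change is needed. The plan leaves a detail out; it does not contradict a claim it has made. It states no power or per-test number that the design then misses, and inadequacy is not shown. Depending on allocation and correlation, the detectable reduction runs from about 8% (30 pairs, ρ = 0.9) to 56% (6 pairs, ρ = 0.3). That range rests on assumed alpha, power, correlation and even spread, and so says more about what is unstated than about a fault.

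Writing down the expected pairs, the visits and the assignment would leave the participants, the data and the estimates as they are. The descriptive summaries in Section III.d already include the number for each continuous outcome, and the raw data are to be listed, so readers will see how many people stand behind each comparison. A sensible analyst will treat a non-significant result from a thinly populated test as inconclusive. The mismatch between five tests and four is a clerical slip: it moves the even-spread average from 6-12 to 7.5-15, and no planned analysis uses the count.

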#### e. HMD descriptions

##### i). ODG R-7 Smartglasses

The ODG R-7 Smartglasses (ODG, San Francisco) uses the camera on the R-7 to obtain scene information for the detection and guidance modules. The detection module identifies places or objects of interest in a scene while tracking and detecting any changes. The guidance module plans an optimal path, based on the detected objects, and guides the user to the destination using audio and/ or vibration feedback.

##### ii). Manually operated auditory feedback and tactile stimulator array

This device allows an operator to control the timing, type, and frequency of feedback provided to the participant. It consists of a custom app, a mobile device (such as a smart phone), an electronics module to communicate with the mobile device and control the user interface, and the user interface, which includes headphones for verbal feedback and a tactile stimulator array for vibrational feedback. The tactile stimulator array will be worn on the head, like a headband, around the waist like a belt, or on the handle of a long cane (used for obstacle detection by visually impaired people). The tactile stimulator array will have 3-5 vibration motors. The entire system is battery powered.

##### iii). Computer Vision Navigation prototyping system

This system will provide the flexibility and capability needed to develop computer vision algorithms for navigation assistance for the visually impaired. The system consists of two components: The Intel RealSense D435i camera and a computer (either an Alienware M15 laptop or a Jetson Mobile Computer). Novel software for detection, mapping, guidance, and recording will be developed and run on the computer. A separate camera for patient tracking may be included. The cameras are connected to the computer via USB cables. The computer is in a backpack or satchel worn by the user. All devices are powered through a battery making this system fully portable. The camera is mounted on the user's head with a head strap. The camera's video is sent to the computer where the computer vision algorithms analyze the scene and decide on a path for the user to follow. The guidance algorithm will send commands to one of several outputs, depending on the experiment. The output devices are 1) the tactile stimulator array 2) audio output of the computer, for verbal guidance commands 3) video output of the device for display on a head-mounted display or as input to the Argus II Video Processing Unit. In the case of the output device being the VPU, the VPU will accept standard video format of NTSC and will stimulate the retina of the patient via the implanted retinal stimulator, according to the received video signal.

